Protocol for the MR CLEAN-Registry (MR CLEAN-R)

A multicenter registry of intra-arterial treatment for acute ischemic stroke

Authors:

[name]¹, [name]¹, [name]³,
[name]², [name]³, [name]¹,
[name]¹, [name]¹,
[name]³, [name]³,
[name]², [name]²

¹Academic Medical Center Amsterdam, departments of neurology and radiology

²Erasmus MC University Medical Center Rotterdam, departments of neurology and radiology

³Maastricht University Medical Center, departments of neurology and radiology

CONTENTS

Acknowledgments 3

Summary 4

1. Introduction and rationale 6

2. Objectives 7

3. Study Design 7

4. Study Population 7

5. Treatment of subjects..... 8

6. Methods 10

7. Safety Reporting 11

8. Statistical analyses 12

9. Ethical considerations, access to appropriate treatment..... 11

10. Administrative aspects and publication 13

11. References 14

12. Tables..... 17

13. Appendices 18

ACKNOWLEDGMENTS

The study is designed, and will be conducted, analyzed and interpreted by the investigators independently of all sponsors.

SUMMARY

RATIONALE AND AIM

After the last inclusion in the MR CLEAN trial there is a momentum in intra-arterial treatment for acute anterior circulation ischemic stroke in the Netherlands. The international guidelines and recommendations allowed intra-arterial treatment as a rescue treatment, but since early 2015, proof of a beneficial effect of intra-arterial treatment on functional outcome is available.

The purpose of the MR CLEAN-R: A post-trial Registry of the Multicenter Randomized Clinical trial of Intra-arterial treatment for acute ischemic stroke in the Netherlands is to monitor implementation and safety of the new intra-arterial treatment in a well-defined set of patients according to explicit criteria, comparable to the MR CLEAN trial population.

MR CLEAN-R is a multicenter registry. In the period following the last inclusion of the MR CLEAN trial this study will register all patients with acute ischemic stroke caused by proximal intracranial occlusion who undergo intra-arterial treatment.

STUDY POPULATION

All patients undergoing intra-arterial treatment for acute ischemic stroke will be registered. The core study population, however, will consist of patients with a clinical diagnosis of acute ischemic stroke, MRI or CT ruling out intracerebral hemorrhage, a score on the National Institutes of Health Stroke Scale (NIHSS) of 2 points or more, a relevant intracranial arterial occlusion, demonstrated by neuro-imaging and the possibility to start intra-arterial treatment within 6 hours after stroke onset. These patients constitute the core study population. Exclusion criteria that pertain to the inclusion in the core study population are similar to the MR CLEAN exclusion criteria. However, all patients undergoing intra-arterial treatment for acute ischemic stroke will be registered.

INTERVENTION

Intra-arterial treatment may consist of intra-arterial thrombolysis with urokinase or alteplase, mechanical treatment or both. Mechanical treatment refers to retraction or aspiration of the thrombus with a catheter guided device, including use of a retrievable stent. The exact choice of intra-arterial treatment modality for each patient is left to the discretion of the local investigator and treating physicians. The steering committee will provide recommendations and guidelines for treatment and selection of patients in the registry. These recommendations may be adjusted to new insights from published observational and controlled studies. Medical management will be delivered according to national standards and guidelines. It may include treatment with intravenous alteplase before inclusion in the registry.

MAIN STUDY OUTCOMES

The primary outcome is the score on the modified Rankin Scale (mRS) 90 days after inclusion in the study. Secondary outcomes are the National Institutes of Health Stroke Scale (NIHSS) score at 24-48 hours,

recanalization (TICI-score), infarct size at 2 days and the occurrence of major bleeding in the first 48 hours after inclusion.

BURDEN AND RISKS ASSOCIATED WITH PARTICIPATION.

All patients participating in the registry will undergo a second CT scan after 2 days, if clinically indicated. All patients will have an interview at three months. Patients undergoing intra-arterial treatment may need sedation or anesthesia and intubation during the procedure. Finally, intra-arterial treatment is associated with increased risk of intra-cerebral hemorrhage. The decision for intra-arterial treatment in a patient will be made by the treating physician on the basis of a professional estimate of the risk and benefits involved.

DISCUSSION

MR CLEAN-R is a post-trial registry of the MR CLEAN trial. Enrollment will start soon after the last inclusion in the MR CLEAN trial (March 17 2014) at least until the eventual start of the next randomized controlled trials. Estimated enrollment period will be April 2014 to at least April 2016. The expected number of registered patients is at least 500.

Key words: alteplase, intra-arterial treatment, acute ischemic stroke, post-trial cohort registry

1. INTRODUCTION AND RATIONALE

1.1 GENERAL INTRODUCTION

In Western Europe and the US, the annual incidence of ischemic stroke is 1-2 per 1000.^{1,2} Half of all patients with stroke die or remain severely disabled. Stroke is one of the major causes of death and the first cause of dependency in the western world. Treatment with intravenous (IV) alteplase, aiming at early reperfusion has been proven effective for these patients, when they are treated within 4.5 hours, and when there are no contra-indications.³⁻⁵ The absolute reduction in the chance of poor outcome in patients treated with IV alteplase within 3 hours from onset amounts to 10%; the number needed to treat is 10.⁶ For the patients treated within 3 to 4.5 hours, this effect is reduced to 7%, for a number needed to treat of 14.⁴

In general, the number of patients eligible for treatment with IV alteplase is limited because of the restricted time window and contra-indications for systemic administration of alteplase. In about 25% of the patients with acute ischemic stroke, symptoms are caused by a proximal occlusion of one of the major intracranial arteries, i.e. the distal intracranial internal carotid artery, the proximal segments of the middle cerebral artery and the anterior cerebral artery.⁷ The likelihood of a proximal intracranial occlusion increases with severity of the neurological deficit at presentation.⁸⁻¹⁰ The effect of IV alteplase in these patients with a symptomatic intracranial arterial occlusion is limited as treatment with IV alteplase leads to recanalization in up to 33% of treated patients only.¹¹ In those without recanalization, outcome is generally poor.^{12, 13}

1.2 EFFECTIVENESS AND SAFETY OF INTRA-ARTERIAL TREATMENT IN RECENT TRIALS

After the last inclusion in the MR CLEAN trial and the start of this Registry there was a momentum in intra-arterial treatment for acute anterior circulation ischemic stroke in the Netherlands. The international guidelines and recommendations allowed intra-arterial treatment as a rescue treatment. During inclusion of patients in this Registry, since early 2015, proof of a beneficial effect of intra-arterial treatment on functional outcome has become available.¹⁴⁻¹⁸ Since then guidelines worldwide have been updated, recommending intra-arterial treatment with stent retrievers as standard therapy in patients with neuro-imaging –confirmed intracranial large vessel occlusion confirmed.^{19, 20}

1.4 RATIONALE: NEED FOR A REGISTRY OF INTRA-ARTERIAL TREATMENT

The purpose of the MR CLEAN-R: A post-trial registry of the Multicenter Randomized Clinical trial of Intra-arterial treatment for acute ischemic stroke in the Netherlands is to monitor intra-arterial interventions for acute ischemic stroke, in order to assess the safety and outcome in clinical practice, in a well-defined set of patients, comparable to the MR CLEAN trial population.

2. OBJECTIVES

To study safety and functional outcome after intra-arterial treatment for acute ischemic stroke caused by thrombo-embolic intracranial occlusion in everyday practice. To identify associations of baseline clinical and neuro-imaging parameters with outcome and adverse events.

3. STUDY DESIGN

This a prospective multicenter registry. At least 17 large hospitals will register patients over a period of at least two years, starting in April 2014. Data of prospectively registered patients after this date, and of patients who died will be entered retrospectively into the database. Actual prospective enrollment will start in January 2015.

4. STUDY POPULATION

4.1 PATIENTS

All patients with acute ischemic stroke of the anterior or posterior circulation who are treated intra-arterial treatment will be registered and followed. Patients who have been included in Randomized Clinical trials will be registered but not data on intervention, clinical and long term follow-up will be entered into the database, in order to maintain the blind.

Patients meeting the inclusion and exclusion criteria as set out below will be entered in the core dataset.

4.2 REGISTRY INCLUSION & EXCLUSION CRITERIA

All patients who underwent IAT for acute ischemic stroke will be registered. We will create a core dataset of patients who conform to specific in- and exclusion criteria, similar to the MR CLEAN trial criteria.

INCLUSION CRITERIA FOR CORE DATA SET

- A clinical diagnosis of acute stroke, with a deficit on the NIH stroke scale of 2 points or more.
- CT or MRI scan ruling out intracranial hemorrhage.
- Intracranial proximal arterial occlusion of a cerebral artery, demonstrated with CTA, MRA or DSA.
- Treatment was started within 6 hours from onset.
- The patient was treated in a MR CLEAN center (list in appendix).
- Age 18 or over.

GENERAL EXCLUSION CRITERIA

- Arterial blood pressure > 185/110 mmHg.
- Blood glucose < 2.7 or > 22.2 mmol/L.
- IV treatment with thrombolytic therapy in a dose exceeding 0.9 mg/kg alteplase or 90 mg.
- IV treatment with thrombolytic therapy despite contra-indications, i.e. major surgery, gastrointestinal bleeding or urinary tract bleeding within the previous 2 weeks, or arterial puncture at a non-compressible site within the previous 7 days.

- Cerebral infarction in the distribution of the relevant occluded artery in the previous 6 weeks.

SPECIFIC EXCLUSION CRITERIA FOR INTENDED MECHANICAL THROMBECTOMY

- Laboratory evidence of coagulation abnormalities, i.e. platelet count $<40 \times 10^9/L$, APTT >50 sec or INR >3.0 .

SPECIFIC EXCLUSION CRITERIA FOR INTENDED INTRA-ARTERIAL THROMBOLYSIS

- History of intracerebral hemorrhage.
- Severe head injury (contusion) in the previous 4 weeks.
- Clinical or laboratory evidence of coagulation abnormalities, i.e. platelet count $<90 \times 10^9/L$, APTT >50 sec or INR >1.7 .
- Current treatment with oral thrombin antagonists, such as argatroban and dabigatran or treatment with oral selective Factor Xa inhibitors, such as rivaroxaban.

EXCLUSION FROM CORE DATA SET

- Violation of one of the preceding in- and exclusion criteria
- Treatment with device without approval of registry steering committee
- Insufficient experience (<5 procedures) with particular type of device
- Treatment in a non-MR CLEAN center.

4.3 PARTICIPATING CENTERS AND CENTER ELIGIBILITY

All centers that have participated in the MR CLEAN trial now participate in the MR CLEAN registry.

As the purpose of the registry is to include all patients had intra-arterial treatment since closure of the MR CLEAN trial, we will also register patients treated in other centers (appendix). These patients will be entered into the extended registry, while we are awaiting a formal procedure for recognition and certification of stroke-intervention centers.

4.4 SAMPLE SIZE

A size of 500 patients allows us to analyze association between outcome such as mRS, neurological deficits (NIHSS) and recanalization and clinical characteristics and imaging at baseline, as well as aspects of the intervention, in multivariable regression models with at most 10 covariates, with sufficient precision.

5. TREATMENT OF SUBJECTS

5.1 INTRA-ARTERIAL TREATMENT

Intra-arterial treatment will consist of arterial catheterization with a microcatheter to the level of occlusion and delivery of a thrombolytic agent and/ or mechanical thrombectomy. Both alteplase and

urokinase for intra-arterial thrombolysis are allowed into the trial, a dose of 1 mg alteplase is considered to be equivalent to 10.000-15.000 U urokinase.²¹ Mechanical treatment may consist of mechanical thrombectomy or thrombus aspiration.

6. METHODS

6.1 STUDY OUTCOMES

PRIMARY OUTCOME

The primary outcome is the score on the modified Rankin Scale at 90 days (Appendix 1).

SECONDARY OUTCOMES

IMAGING PARAMETERS

- Infarct size assessed by CT at 2 days, when available. This includes manual tracing of the infarct perimeter and semi-automated pixel thresholding.^{22, 23}
- Pre-treatment and post-treatment TICl-score assessed on DSA acquired intervention.

CLINICAL PARAMETERS

- NIHSS at 24-48 hours days or at discharge.

FUNCTIONAL OUTCOME

Functional outcome will be assessed by means of the modified Rankin Scale at 90 days, this is done routinely in our centers, as standard of care.

SAFETY PARAMETERS

Safety is an issue of concern, as the experience with the intervention, overall, and within the participating centers, is limited. Safety parameters include hemorrhagic complications, and short-term outcome (mortality, NIHSS at 24-48 hours). As we will make use of web-based data-entry, these data will be available on short notice.

The primary safety parameter will be neurologic deterioration within 24 hours from inclusion in the registry. Neurological deterioration is defined as any decline in NIHSS of 4 points or more. In these patients, urgent brain CT is mandatory. This serious adverse event will be further classified as due to intracranial hemorrhage, ischemia or other (undetermined) cause. A full list of serious adverse events is provided in Appendix 5.

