6.3 STUDY PROCEDURES

BASELINE DATA OBTAINED AT ADMISSION

Clinical data, neuro-imaging data, data that might be related to treatment effect or to adverse events caused by the intervention, as well as several stroke risk factors, will be recorded in order to illustrate the representativeness of the study population (Table 1.1).

INCLUSION AND REGISTRATION

The registry office will be notified when a new patient is entered into the web-based database. Personal data will be sent to the registry office separately, through scrambled email.

FOLLOW-UP DATA

NIHSS scores at baseline and after 24-48 hours will be scored constructed from clinical data when missing. All patients will undergo CT or MR imaging at 2 days, if clinically indicated. Raw data will be forwarded to the trial office for blind evaluation. When there was no three month follow-up to determine mRS at three months, mRS score will be derived of discharge data or data from closed follow-up at another moment.²⁴

WITHDRAWAL

Patients can stop compliance with the registry at any time for any reason if they wish to do so without any consequences. **Every attempt will be made to complete follow-up in these patients. All patient data will be stored without identifying parameters.**

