9.3 BURDENS TO THE PATIENT

All patients will undergo an additional CT scan after 2 days to assess infarct size, if clinically indicated. Radiation exposure for this CT scan is 2.1-2.3 mSV (milliSievert).²⁶

Patients may be asked to participate in substudies (see section 10.2). Also, during the intervention aspirated blood may be kept and stored, as well as the thrombo-embolic material which is retrieved from the retraction devices (THRAPS substudy).

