1. STUDY PARAMETERS

1.2 Follow-up	
Treatment	Pre- and post intervention TICI-score, duration of procedure, actual mode of treatment
Clinical assessment at 24-48 hours	Clinical status, NIH Stroke Scale, NIHS supplemental motor scale
Neuro-imaging at 2 days (if clinically indicated)	Plain CT: location, ASPECTS score, hemorrhagic transformation (NINDS/ECASS classification), hyperdense artery sign.
Clinical assessment at 90 days	Modified Rankin Scale
Serious adverse events	See appendix 5

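### Infarct size at 2 days is a secondary outcome, but the scan is made only on clinical indication, so results from available scans describe a selected subset

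*Protocol*

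**What the plan says.** The Summary (Main study outcomes) names among the secondary outcomes "infarct size at 2 days and the occurrence of major bleeding in the first 48 hours after inclusion", with no subset attached. Section 6.1 repeats the outcome with a qualifier: "Infarct size assessed by CT at 2 days, when available".

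Four places state when the scan is made, and they agree:

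- Summary, Burden and risks: "All patients participating in the registry will undergo a second CT scan after 2 days, if clinically indicated".
- Section 6.3, Follow-up data: "All patients will undergo CT or MR imaging at 2 days, if clinically indicated".
- Section 9.3: "All patients will undergo an additional CT scan after 2 days to assess infarct size, if clinically indicated". This sentence ties the scan to infarct size explicitly.
- Table 1.2 puts the same condition on the row for 2-day neuro-imaging. That row also holds follow-up ASPECTS and hemorrhagic transformation.

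For the primary safety parameter, which covers the first 24 hours, section 6.1 states: "Neurological deterioration is defined as any decline in NIHSS of 4 points or more". It adds: "In these patients, urgent brain CT is mandatory".

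Section 8 analyses associations of patient characteristics and intervention details with the secondary outcomes, using conventional tests and multivariable regression. It names no separate population for the outcomes read from the 2-day scan.

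**The concern.** A scan made on clinical indication is more likely in a patient who is doing badly, and a patient who is doing badly is more likely to have a large infarct. Whether the outcome is observed is then related to its value. The qualifier in section 6.1 tells the reader that some scans will be missing. It does not say that the missingness follows the clinical course, or that the results describe scanned patients only.

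Two results are at stake. The first is the descriptive one: average infarct size, and the proportion with hemorrhagic transformation, after treatment in everyday practice. The second is the set of associations between baseline or procedural factors and infarct size, which belongs to the second objective in section 2. Selecting patients on a consequence or correlate of the outcome can distort both.

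**Working it through.** **What the protocol gives.** The only nearby figure is the 500 patients with at most 10 covariates in section 4.4. That statement does not name infarct size among its outcomes and gives no standard deviation, effect size or share of patients scanned. There is no figure of the plan to reproduce, and the size of the bias cannot be derived from the document. What follows is illustration. Every input except N = 500 is an assumption.

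**1. Mean infarct size, two groups.** Assume 20% of patients deteriorate (mean 120 mL, 95% scanned at day 2) and 80% are stable (mean 40 mL, fraction c scanned).

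- True mean: 0.2 × 120 + 0.8 × 40 = 56 mL.
- Mean among scanned: (0.2 × 0.95 × 120 + 0.8 × c × 40) / (0.2 × 0.95 + 0.8 × c) = (22.8 + 32c) / (0.19 + 0.8c).

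| c | Mean among scanned | Against 56 mL |
|---|---|---|
| 0.3 | 32.4 / 0.43 = 75.3 mL | +35% |
| 0.5 | 38.8 / 0.59 = 65.8 mL | +17% |
| 0.7 | 45.2 / 0.75 = 60.3 mL | +8% |

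**2. The same formula with early deaths.** Suppose deaths before day 2 cut scanning of deteriorating patients to 60%, while 70% of stable patients are scanned. The mean among scanned is (0.2 × 0.6 × 120 + 0.8 × 0.7 × 40) / (0.12 + 0.56) = (14.4 + 22.4) / 0.68 = 54 mL, just below 56. In this two-group setting the sign reverses exactly when deteriorating patients are scanned less often than stable ones.

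**3. In standard-deviation units.** Let q be the share with a poor course, p₁ and p₀ the scan rates in poor-course and good-course patients, and d the difference in infarct size between them in SD. The poor-course share among scanned patients is s = q·p₁ / (q·p₁ + (1 − q)·p₀), and the bias of the mean is (s − q)·d.

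- Mildest case run: q = 0.3, p₁ = 0.95, p₀ = 0.7, d = 0.5. About 387 of 500 are scanned, s = 0.285 / 0.775 = 0.368, and the bias is 0.068 × 0.5 = 0.03 SD.
- Strongest case run: q = 0.3, p₁ = 0.9, p₀ = 0.3, d = 1.0. Here 240 of 500 are scanned, s = 0.27 / 0.48 = 0.563, and the bias is 0.263 × 1.0 = 0.26 SD.
- With p₁ = p₀ = 1 the bias is 0.

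**4. Associations.** In a simulation of 2,000,000 draws with a true standardised slope of 0.30, the probability of a scan rose with infarct size itself through a logistic function.

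| Fraction scanned | Estimated slope |
|---|---|
| 100% | 0.301 |
| 70%, weaker dependence | 0.262 |
| 50%, weaker dependence | 0.254 |
| 50%, stronger dependence | 0.198 |
| 43%, stronger dependence | 0.191 |

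A separate simulation of 400,000 patients used the mechanism of step 1, with scanning driven by deterioration. The unweighted association was 1.01 to 1.05 times the full-cohort value, and weighting by the probability of imaging brought the ratio to about 1.00. The damage to associations, and how far weighting repairs it, therefore depend on whether scanning follows recorded clinical variables or infarct size beyond them.

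**The case against.** **The restriction is disclosed and deliberate.** This is a registry of routine care, infarct size is one of several secondary outcomes, and section 6.1 carries the qualifier that the Summary lacks. That stands, and it keeps the point modest. Disclosing that scans will be missing does not, however, name the population to which the results apply.

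**Missing-data handling belongs in a statistical analysis plan.** Such a plan may exist and is not shown, so its absence is no fault here. Nor does section 8 expressly prescribe an available-case analysis. The point rests on what the protocol itself fixes: an outcome, a measurement rule that depends on clinical course, and ordinary tests and regression with no subset named. Carried out as written, these give available-case results.

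Four stronger readings are tempting, and the document does not support them:

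- *Deteriorating patients must have the infarct-size scan.* The mandatory urgent CT belongs to deterioration within 24 hours of inclusion. Nothing says that it serves as the 2-day scan or is used to measure infarct size. It shows only that imaging follows clinical course; the conditional 2-day scan carries the argument.
- *Infarct size will be overstated.* Upward bias is the likelier direction, but patients who die before day 2 have no scan and probably had large infarcts. Step 2 of the working shows that the sign can reverse.
- *All imaging outcomes are affected.* TICI is read from angiography at the intervention and does not depend on the 2-day scan.
- *Comparisons between centres are invalid.* The protocol plans no such comparison. Differing scan habits are a reason to report the scanned fraction by centre, and no more than that.

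**Weighting is no cure if scanning depends on infarct size itself.** This is correct. Weights or imputation remove only selection explained by the recorded variables, and the fix has to say so.

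**Conclusion.** The point holds as a limited one. The protocol lists 2-day infarct size as a secondary outcome and obtains it through a scan whose presence depends on the course after treatment. Summaries and associations from available scans describe a selected subset and can be biased. The same applies to the follow-up ASPECTS and hemorrhagic transformation in Table 1.2.

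No size can be attached from the document. Under the assumptions shown, the error in the mean ranges from slightly negative (54 against 56 mL) to +35%, or 0.03 to 0.26 SD in the second parametrisation. Associations range from nearly unaffected (1 to 5%) to clearly attenuated (0.30 falling to 0.19). The primary outcome is untouched. The change is worth making because it is cheap and because an unlabelled infarct-size result would be read as applying to the whole registry.

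**What to change.** In sections 6.1 and 8, for infarct size, follow-up ASPECTS and hemorrhagic transformation:

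1. Define the target population as patients alive at the 2-day time point, and report deaths before imaging separately. This avoids imputing a 2-day infarct size for patients who had already died.
2. Label the unweighted result as scanned patients only. Report the scanned fraction overall, by centre and by deterioration status.
3. Add an analysis weighted by the inverse probability of imaging, or a multiply imputed one. Use variables already recorded: baseline and 24-48 hour NIHSS, deterioration, post-procedure TICI, age and centre.
4. State that this analysis corrects only the selection explained by those variables.

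The cost is wording, modest programming and somewhat wider intervals. No extra scans and no change in care are involved.

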5. ADVERSE EVENTS

1. Neurological deterioration
2. Symptomatic intracranial hemorrhage
3. Extracranial hemorrhage requiring surgery or blood transfusion

4. Technical complications at the target lesion such as perforation or dissection
5. Aspiration pneumonia and other infections, deep venous thrombosis and pulmonary embolism
6. Allergic reaction towards contrast fluid
7. Death from any cause within the registry period

An adverse event is considered serious when it causes mortality, is life-threatening, requires prolonged hospitalization, or results in persistent significant disability.

AMENDMENTS

AMENDMENT NO 1

February 15, 2016

Whole protocol: Barthel index and EQ5D are deleted from this protocol and not done in the Registry. Therefore every mention of this scores was deleted.

Page 1 the subtitle: "A multicenter registry of intra-arterial treatment for acute anterior circulation ischemic stroke" was changed into:

"A multicenter registry of intra-arterial treatment for circulation ischemic stroke"

At 'Authors' [name] was added.

Page 4: we replaced of 'Rational and aim' the first paragraph "After the last inclusion in the MR CLEAN trial there is a momentum in intra-arterial treatment for acute anterior circulation ischemic stroke in the Netherlands. The international guidelines and recommendations allow intra-arterial treatment as a rescue treatment, but proof of a beneficial effect of intra-arterial treatment on functional outcome is not available. New approaches to treatment that make use of stent-retrievers however, show promising results. Until the results of trials that make use of these stent-retrievers are known, clinicians will be inclined to use these devices on selected patients, especially on those that do not respond to or have contraindications for treatment with intravenous thrombolytics." with:

"After the last inclusion in the MR CLEAN trial there is a momentum in intra-arterial treatment for acute anterior circulation ischemic stroke in the Netherlands. The international guidelines and recommendations allowed intra-arterial treatment as a rescue treatment, but since early 2015, proof of a beneficial effect of intra-arterial treatment on functional outcome is available.¹⁴⁻¹⁸"

Furthermore on this page in the section 'study population' we changed "anterior circulation stroke" in "acute ischemic stroke" in both the first and last sentence.

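### The primary safety parameter cannot count a patient who dies within 24 hours without a second NIHSS, and missing baseline NIHSS may be constructed with the outcome known

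*Protocol*

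**What the plan says.** **Event.** Protocol section 6.1 (Safety parameters) states: "The primary safety parameter will be neurologic deterioration within 24 hours from inclusion in the registry". The next sentence gives the whole definition: "Neurological deterioration is defined as any decline in NIHSS of 4 points or more". Each such event is to be classified as due to intracranial haemorrhage, ischaemia or another cause. Death is not mentioned in the definition.

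**Schedule.** Table 1.2 places the follow-up NIHSS under "Clinical assessment at 24-48 hours", and the secondary outcome in section 6.1 is "NIHSS at 24-48 hours days or at discharge".

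**Deaths elsewhere.** Mortality is a short-term safety parameter of its own in section 6.1. Section 7.1 lists death among the expected serious adverse events up to the 90-day assessment. In Appendix 5, neurological deterioration is item 1 and item 7 is "Death from any cause within the registry period". Appendix 1 gives death category 6 of the mRS.

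**Missing scores.** Section 6.3 (Follow-up data) states: "NIHSS scores at baseline and after 24-48 hours will be scored constructed from clinical data when missing". It names no assessor, source limit, time limit, masking or flag. Section 6.2 states masked assessment for neuroimaging, and describes blinding as keeping baseline and treatment details from the person who assesses outcome.

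**Retrospective entry.** Section 3 provides that data of prospectively registered patients "and of patients who died will be entered retrospectively into the database", and section 9.2 refers to patients recruited retrospectively since April 2014.

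**The concern.** Two rules fixed in the protocol affect how the NIHSS can be used.

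First, a change score needs two scores. A patient who dies before a second one is recorded cannot meet the definition, so one of the worst early courses drops out of the measure chosen as primary for safety. Such a death also gets no cause classification under this parameter. If early deaths took the place of survivable deteriorations, the rate would fall.

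Second, baseline NIHSS has several uses. It is a listed baseline characteristic (Table 1.1), one of the clinical factors to be related to outcome (section 2), the reference for the 4-point change, and part of the core data set criteria (section 4.2). If it is built from the whole record after the outcome is known, the score may absorb some of that knowledge. An association between baseline severity and outcome would then partly reflect how the score was made.

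**Working it through.** The protocol states no rate for this parameter, so there is no figure of its own to reproduce. The check is a reading of the rules, followed by an illustration on assumed rates.

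**1. Can an early death be an event?**
- The window is 24 hours from inclusion. The next planned NIHSS is at 24-48 hours. If both run from inclusion, no planned score falls before the end of the window.
- An unscheduled score taken before death can show the 4-point change, and such a patient is an event.
- Construction from clinical data could supply a 24-48 hour score for a patient alive at that time. It cannot supply one for a patient already dead.
- What remains is the patient who dies within 24 hours with no second recorded score. No sentence makes that patient an event.

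**2. How much could this move the rate?** Assumptions, not from the protocol: a proportion p = 10% of scored patients deteriorate, and a proportion d = 1%, 3% or 5% of all patients die within 24 hours unscored.
- Deaths counted as events: (1 − d) × p + d
- Deaths counted as non-events: (1 − d) × p
- Deaths left out of the denominator: p

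| d | Deaths as events | Deaths as non-events | Deaths left out |
|---|---|---|---|
| 1% | 0.99 × 0.10 + 0.01 = 10.9% | 9.9% | 10.0% |
| 3% | 0.97 × 0.10 + 0.03 = 12.7% | 9.7% | 10.0% |
| 5% | 0.95 × 0.10 + 0.05 = 14.5% | 9.5% | 10.0% |

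The gap is exactly d if deaths are non-events (1.0, 3.0 and 5.0 points) and d × (1 − p) if they are left out (0.9, 2.7 and 4.5 points). At d = 5% the relative shortfall is 5.0/14.5 = 34% or 4.5/14.5 = 31%; at d = 1% it is 1.0/10.9 = 9% or 0.9/10.9 = 8%. The absolute gap against the non-event reading does not depend on p, but the relative one does. With p = 5% and d = 4%, the rates are 0.96 × 0.05 = 4.8% and 4.8% + 4.0% = 8.8%, so 4.0/8.8 = 45% of the combined events are missed.

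**3. Can the scorer know the outcome when constructing baseline NIHSS?**
- Section 6.3 allows construction for baseline as well as follow-up and does not restrict the source to admission records.
- Sections 3 and 9.2 allow entry after the fact, including for patients who died. Section 3 puts the start of registration in April 2014 and of actual prospective enrolment in January 2015.
- The amendment that added the construction rule is dated February 15, 2016, 22 months after April 2014. Patients treated more than 90 days before that date had already passed the primary outcome time point.
- Section 6.2 protects outcome assessment from baseline knowledge. It does not address the reverse.

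Knowledge of the outcome is therefore permitted. The protocol gives no count of constructed scores, so no size can be computed.

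**The case against.** The strongest reply is that the protocol describes event reporting, not a subtraction of two scheduled scores. Any qualifying decline counts, it is a serious adverse event, and it goes into a cumulative log. A patient who worsens on record before dying already qualifies. This stands, and it confines the gap to deaths within 24 hours with no second recorded score.

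It is also true that early deaths are captured elsewhere: as mortality, as serious adverse events and as mRS 6. A reader might infer that the registry as a whole understates early harm. The protocol does not support that; only this one parameter is affected. Keeping death apart from neurological deterioration is a legitimate choice, and merging them brings in non-neurological deaths. But the choice should be stated, since this is the parameter named primary for safety.

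On construction, late data entry is not the same as late scoring, and the rule applies only to missing scores. A prospectively registered patient may well have a score made at admission. A reader might infer that associations with baseline severity are inflated, or that the 2-point core criterion is distorted. Neither is shown: the protocol permits outcome-aware scoring but gives no frequency and no evidence of direction.

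Finally, a reader might conclude that the 24-48 hour NIHSS analysis is restricted to survivors. The protocol does not say so. It is silent on deaths there, and a statistical analysis plan may settle the matter. The event definition and the construction rule are different, because both are stated in the protocol and govern how the data are made. A later analysis plan cannot undo scores already constructed unmasked and unflagged.

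**Conclusion.** The point holds in a limited form. As defined, the primary safety parameter cannot register a death within 24 hours in a patient with no second recorded NIHSS, although that death is reported elsewhere. Separately, section 6.3 permits a missing baseline NIHSS to be constructed by someone who knows the outcome, which could bias the associations that the registry sets out to estimate.

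On the assumed 10% deterioration and 1-5% unscored deaths, the reported rate would be about 1-5 percentage points below the rate with deaths counted. The top is an upper bound: it needs 5% of all patients to die within 24 hours, none with a recorded 4-point worsening, and all of them counted as non-events. For the construction rule, neither direction nor size can be given. Both are cheap to repair and worth repairing; neither undermines the registry's primary outcome, in which death has its own category.

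**What to change.** - **Section 6.1.** For reporting, define the parameter as an NIHSS worsening of 4 points or more, or death, within 24 hours of inclusion. Show deaths separately and by cause beside the combined rate. Leave the clinical instruction on CT as it stands. Writing worsening also removes an ambiguity: section 4.2 treats NIHSS points as deficit, so a decline read literally is an improvement.
- **Section 6.3.** Construct a missing baseline NIHSS only from admission records made before treatment. Flag every constructed score in the database, and repeat the main models without them.
- **24-48 hour NIHSS.** State how deaths are handled, in the protocol or the analysis plan. Worst rank is one option, not the only correct one.

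The cost is a few sentences, one database flag and one sensitivity analysis. The combined rate will be slightly less favourable and will include some non-neurological deaths, which is why the separate display by cause is needed. Restricting the source may leave some baseline scores missing. If constructed scores are commoner in patients who died, dropping them also changes the case mix, so a difference between the two sets of models should not be read as scoring bias alone.
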